11.1.4 Immune Response Set (IRS)

The IRS includes all subjects who received the IMP at least once and from whom data on at least one immune response endpoint were obtained after the start of IMP administration.

11.2 Handling of Data

Baseline is defined as the last available screening or pre-treatment assessment.

If a problematic subject or data are encountered, the sponsor will decide how to handle the subject or data, with advice from the medical expert, as necessary.

11.3 Analysis Items and Method

11.3.1 Efficacy Analysis

FAS will be used as the primary analysis population and PPS will be used as the secondary analysis population to assess the stability.

Regarding the judgment of relapse which will be used in the primary endpoint, the percentage of leukemic blast cells and other differential white blood cell counts in the prepared specimen will be measured at the trial site and the central pathological review committee will evaluate and verify the judgment of relapse by the trial site. The final judgment from the central pathological review committee will be taken as the main evaluation criteria.

11.3.1.1 Primary Endpoint

1) Definition

- Disease-free survival (DFS)
 - Observation period: For each subject, the time from randomization to the DFS-cutoff date. The DFS-cutoff date was set as the completion date of each subject.
 - Definition: The time from randomization until relapse or death from any cause, whichever comes first by the DFS-cutoff date.
 - Event: Relapse or death from any cause by the DFS- cutoff date.
 - Censoring:
 - If an event has not been observed by the DFS-cutoff date, then the last confirmed non-relapse date will be used as the censoring date.
 - For subjects who have withdrawn from this trial before the completion date for reasons other than relapses or deaths, if non-relapse has been confirmed on the withdrawal date, then the withdrawal date will be used as the censoring date.

2) Analysis Set

FAS, PPS

3) Analysis Method

Primary method: Kaplan-Meier curve, log-rank test

The Kaplan-Meier method will be carried out to estimate DFS functions and plot the DFS curve by treatment arm.

- The log-rank test will be used to determine whether there are differences at the 5% significance level in DFS between the OCV-501 treatment arm and the placebo arm.
- The hazard ratio (OCV-501 vs. placebo) and its 95% confidence interval will be calculated using the wald test.
- The 2-year survival rate and median survival time will be calculated and 95% CI of survival rate will be calculated using the Greenwood formula.

Exploratory method:

- Harrington-Fleming Test: applying the weight $1-S(t)$, where $S(t)$ is calculated from Kaplan Meier survival estimate.
- HR and its 95% CI will be calculated at every 3-month interval. The hazard rate will be calculated using the person-year method by treatment arm.
- The Cox PH (Proportional Hazards) model will be used to adjust treatment comparison for a set of covariates which are set to be country (each country) and age (60 to 64 years, 65 to 70 years, and ≥ 71 years) on the time-to-event variable. Also, the assumption that the hazard ratio is constant over time will be graphically assessed by looking at the log-minus-log survival plots with stratification of covariates.

11.3.1.2 Secondary Endpoints

1) Definition:

- Overall survival (OS)
 - Observation period: For all subjects, the time from randomization to OS-cutoff date. The OS-cutoff date was set as the date after 728 days (2 years) from the day that the last subject started IMP administration without consideration of withdrawal by the OS-cutoff date.
 - Definition: The time from randomization until death from any cause by the OS-cutoff date.
 - Event: Death from any cause by the OS-cutoff date.
 - Censoring:
 - If an event has not been observed by the OS-cutoff date, then the last confirmed survival date will be used as the censoring date.

• Quality of life (QOL)

Global health status
Functional Scale: Physical Role Cognitive Emotional Social
Symptom Scale: Fatigue Pain Nausea/vomiting
Single Items: Dyspnea Sleep disturbance Appetite loss Constipation Diarrhea Financial impact

• Performance status (PS)

2) Analysis Set

FAS, PPS

3) Analysis Method:

- Overall survival (OS)

Primary method: Kaplan-Meier curve, log-rank test

The Kaplan-Meier method will be carried out to estimate the OS function and plot the OS curve of each treatment arm.

- The log-rank test is used to determine whether there are differences at the 5% significance level in OS between the OCV-501 arm and the placebo arm.
- The hazard ratio (OCV-501 vs. placebo) and its 95% confidence interval will be calculated using the wald test.
- The 2-year survival rate and median survival time will be calculated and 95% CI of survival rate will be calculated using the Greenwood formula.

Exploratory method:

- Harrington-Fleming Test: applying the weight $1-S(t)$, where $S(t)$ is calculated from Kaplan Meier survival estimate.
 - HR and its 95% CI will be calculated at every 3-month interval. The hazard rate will be calculated using the person-year method by treatment arm.
 - The Cox PH (Proportional Hazards) model will be used to adjust treatment comparison for a set of covariates which are set to be country (each country) and age (60 to 64 years, 65 to 70 years, and ≥ 71 years) on the time-to-event variable. Also, the assumption that the hazard ratio is constant over time will be graphically assessed by looking at the log-minus-log survival plots with stratification of covariates.
- Quality of Life (QOL)
At each time point, the scores and changes from baseline will be summarized using descriptive statistics by treatment arm. Changes from baseline at each time point will be plotted by trend diagram.

At each time point, the treatment effect will be estimated using the difference of change between the least squares means (adjusted means) of each treatment arm.
- Performance Status (PS)
Frequency distributions at each time point will be calculated in the OCV-501 arm and the placebo arm.

11.3.2 Safety Analysis

1) Definition:

AEs, clinical laboratory tests, vital signs (blood pressure, pulse rate, body temperature), urinalysis, body weight, and electrocardiogram.

2) Analysis Set:

SS

3) Analysis Method

The analysis will be performed by each treatment arm.

Descriptive statistics will be calculated for continuous variables and frequency distributions at each time point will be calculated for categorical variables.

The object of analysis is AE occurrence after the start of IMP administration. AEs will be categorized using the terminology of the Medical Dictionary for Regulatory Activities (MedDRA). AEs will be tabulated by System Organ Class (SOC) and Preferred Term (PT), with PT substituted for verbatim terms. The number of subjects and number of incidence of the following events will be tabulated per arm. A summary of SAEs will be provided by severity.

- Adverse events
- Adverse drug reactions
- Serious adverse events by severity
- Adverse events leading to withdrawal

Severity will be graded using Common Terminology Criteria for Adverse Events (CTCAE) version 4.0.

4) Safety Interim Analysis

For the purpose of data safety monitoring, the safety interim analysis will be conducted regularly on all subjects to provide AE tables, SAE lists, etc, while the level of blinding is being maintained.

11.3.3 Exploratory Items Analysis

1) Definition:

OCV-501 specific IFN- γ production, WT1-killer peptide specific IFN- γ production, anti-OCV-501 antibody level, anti-WT1 antibody level, WT1 mRNA level and immunoglobulin.

2) Analysis Set:

IRS

3) Analysis Method:

Generally, a summary will be provided in terms of the mean, geometric mean, standard deviation, median, minimum, maximum and number of patients, unless otherwise stated. Trend diagrams will be plotted by subject.

For WT1 mRNA item, the change from baseline at each time point will be log-transformed and t-test will be conducted between two treatment arms. At each time point, a summary of descriptive statistics will be provided and trend diagrams will be plotted by subject.

11.3.4 Demographic and Other Baseline Characteristics

1) Definition:

Age, sex, height, body weight, diagnosis of AML (WHO classification), regimen of induction therapy, regimen of consolidation therapy, duration from the last dose of consolidation therapy to randomization, maximum WT1 mRNA level at AML diagnosis or at the time of induction therapy or consolidation therapy, and country where the trial was conducted.

2) Analysis Set:

FAS, PPS, SS

3) Analysis Method:

Frequency distribution or descriptive statistics for each variable will be calculated according to the nature of the data (continuous or discrete).

11.3.5 Extent of Exposure

1) Definition:

Duration of exposure to treatment (days), full dose, total number of doses

2) Analysis Set:

SS

3) Analysis Method:

A summary of the duration of exposure to treatment and total dose will be provided. The descriptive statistics will be calculated by treatment arm.

Duration of exposure to treatment will be calculated in days as follows:

$$\text{IMP administration end date} - \text{IMP administration start date} + 1$$

11.3.6 Significance Level and Confidence Interval

Two-sided statistical tests will be conducted at the 5% significance level and 95% confidence interval will be provided.

11.3.7 Subgroup Analysis

1) Definition:

The primary endpoint DFS and secondary endpoint OS will be examined for the following subgroups.

Factor	Categories
Country/ region	Japan, Republic of Korea, and Taiwan
Age	60 to 64 years, 65 to 70 years, ≥ 71 years

2) Analysis Set:

FAS

3) Analysis Method:

For each subgroup, summaries and statistical analysis will be conducted by treatment arm as follows.

- The Kaplan-Meier method will be carried out to estimate the survivor function and plot the survival curve by treatment arm.
- The hazard ratio (OCV-501 vs. placebo) and its 95% confidence interval will be calculated using the wald test
- The 2-year survival rate and median survival time will be calculated and 95% CI of survival rate will be calculated using the Greenwood formula.

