1.2.3 Trial Rationale

OCV-501 is a drug product containing an HLA class II restricted WT1 derived peptide. In in vitro pharmacology studies, OCV-501 has demonstrated significant induction of OCV-501-specific Th1 cells and CTLs in PBMC from healthy adult donors,²⁰ and significant induction of interferon (IFN- γ) production from OCV-501-specific T cells in a dose-dependent manner. The activation effect on OCV-501-specific T cells was HLA class II restricted.^{20,21} In the presence of OCV-501-specific T cells, the addition of OCV-501 increased the number of co-existing WT1 killer peptide-specific CTLs.²²

Because WT1 expresses frequently in patients with AML^{11,12,23} and AML patients often show an increased number of WT1-specific CTLs in comparison with healthy donors,²⁴ OCV-501 is being developed as an AML therapy product. It is expected that normal

Protocol No. 311-12-001

leucocytes will have recovered and there will be fewer leukemia cells in patients who have completed consolidation therapy. Therefore, AML patients who have completed consolidation therapy were set as the target trial subjects.

In the phase 1 trial (Trial 311-10-001), OCV-501 was subcutaneously administered once a week for 4 times at doses of 0.3 mg, 1 mg, and 3 mg in elderly AML patients and safety and tolerability of OCV-501 were assessed. In this phase 1 trial, no DLTs were reported and the tolerability of OCV-501 treatment up to a dose of 3 mg was confirmed. In addition, OCV-501 specific DTH was observed at each dose. This finding suggests that OCV-501 induces the T cell mediated immune response. See Section 3.2, for the rationale of setting the trial design, dose, regimen, and primary endpoint.

This trial is planned as a randomized placebo-controlled comparative trial, to assess the efficacy and safety of OCV-501 treatment as a maintenance therapy in elderly patients with AML who have completed consolidation therapy after being judged to have achieved CR following an induction regimen. In the ongoing phase 1 extension trial (Trial 311-10-002), drug allergy was observed for one patient and it was considered that a causal relationship between the adverse event (AE) and OCV-501 could not be ruled out. Therefore, in this phase 2 trial, patients' general conditions, including injection site reaction, will have to be observed at the trial site for one hour after IMP administration.

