3.3.3 Exploratory

- OCV-501-specific IFN- γ production, WT1-killer peptide specific IFN- γ production, anti-OCV-501 antibody level, anti-WT1 antibody level and immunoglobulin
- WT1 mRNA level

[Rationale for endpoint selection]

[Efficacy]

Primary endpoint

This trial was planned to assess the contribution of OCV-501 to life prognosis through relapse prevention in AML patients who have completed consolidation therapy. Therefore, disease-free survival (DFS: time from randomization to AML relapse or death from any cause, whichever comes first, within the observation period) was set as the primary endpoint.

Secondary Endpoints

Overall survival (OS) was set as a general endpoint relevant to survival in anticancer drug therapy. The representative QOL and performance status surveys, EORTC QLQ-C30 and ECOG PS, were set to assess QOL and PS in subjects.

[Safety]

General tests were set out of consideration for subjects' safety and to assess the safety of OCV-501.

[Exploratory]

Measurements of OCV-501-specific IFN- γ production and WT1-killer peptide specific IFN- γ production were set to measure the helper T cell activation and WT1-killer specific T cell activation induced by OCV-501. Measurements of anti-OCV-501 antibody level and anti-WT1 antibody level were set to confirm antibody induction ability because antibody induction against the WT1 protein has been reported.³⁴ Immunoglobulin was set to monitor whole immunological changes.

Expressed level of WT1 mRNA was set because it is considered to be useful as a monitoring marker of minimal residual disease (MRD).

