5.2 Inclusion Criteria

Patients who meet all of the following criteria at the time of enrollment will be selected.

- 1) Patients with AML (WHO classification 2008) patients who achieved first complete remission within one or two courses of standard induction therapy*, and completed standard consolidation therapy* (one or more courses).
* Induction therapy and consolidation therapy are according to the institution's standard of care.
 - Applicable types of disease for this trial in WHO classification
 - AML with recurrent genetic abnormalities
 - AML, myelodysplasia-related changes
 - AML, not otherwise specified
- 2) Patients who are 60 years or older at the time of providing informed consent
- 3) Sex: Male or female
- 4) Patients with an Eastern Cooperative Oncology Group (ECOG) performance status of 0 - 2 at the time of trial enrollment
- 5) Patients with no significant impairments in the functions of major organs (as indicated by laboratory values) meeting the following criteria within 3 weeks of IMP administration:
 - Hematological functions
 - Patients must not require administration of a blood-derived product or blood transfusion, or granulocyte colony-stimulating factor (G-CSF), granulocyte macrophage colony-stimulating factor (GM-CSF)
 - Neutrophil count: $> 1,000/\mu\text{L}$
 - Platelet count: $> 50,000/\mu\text{L}$
 - Hepatic functions
 - AST and ALT: $< 5 \times$ the upper limit of normal (ULN)
 - Total bilirubin: $< 3 \times$ ULN
 - Renal function
 - Serum creatinine: $< 3 \times$ ULN
- 6) Patients with a life expectancy of at least 3 months
- 7) Patients who have provided written informed consent within 90 days from the last dose of consolidation therapy on an informed consent form that has been approved by an institutional review board or independent ethics committee.

[Rationale for Inclusion Criteria]

- 1) The WHO classification is used for the definition of AML and corresponding types of disease are specified.
Elderly AML patients with therapy-related myeloid neoplasms have an especially poor prognosis and it is expected that AML will relapse at an early point in those patients. Considering the pharmacological profile of OCV-501 that exerts therapeutic efficiency through boosting immune response, patients with therapy-related myeloid neoplasms were excluded.

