11.5 Rationale for Target Number of Patients

The number of AML patients is not very high, and is estimated to be approximately 7000 in Japan³⁶. From the fact that in the previous clinical trial (JALSG GML200) in elderly AML patients, it has been forecast that the possible enrollment in Japan is to be at most 70 in one year. Also, from the preliminary trial feasibility survey, it is known that around 50 subjects could be recruited in one year in Republic of Korea and Taiwan. Through a global trial in Japan, Republic of Korea and Taiwan, it is considered possible to enroll 120 subjects in one year to assess the efficacy of OCV-501.

Within the limitation of the past experiences with regard to IMP administration, the target sample size will be considered with reference to following publications^{25,26,27,37}. With reference to disease-free survival which has been reported from trials in AML subjects 60 years or older who have received the consolidation therapy followed by the maintenance therapy, the 2-year DFS rate of placebo arm has been estimated to be around 20%.^{25,26,27} On the other hand, considering the so-called graft-versus-leukemia (GVL) effect associated with a lower relapse risk after the allogeneic hematopoietic stem cell transplantation, OCV-501 is basically expected to have the same benefits. With reference to the findings of Kurosawa et al,³⁷ which have reported a 30% higher 2 or 3-year DFS in elderly AML subjects who have received the allogeneic hematopoietic stem cell transplantation compared with those without transplantation, OCV-501 is expected to have a 15% - 20% higher 2-year DFS. Under the assumption of exponential distribution of DFS time, the hazard ratio (placebo vs. OCV-501) has been set to 0.57 - 0.65, and with a two-sided log-rank test at the 5% significance level, 60 or more subjects in each treatment group can achieve a power of 53 to 75% or more to detect the difference between placebo and OCV-501 groups.

12 Quality Control and Quality Assurance for the Trial

To ensure the quality of the trial, trial sites, contract research organizations, laboratories performing clinical tests, and the sponsor will perform quality control for the trial according to their respective Standard Operating Procedures.

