 - In the model of Cox analysis, treatments effect will be adjusted with covariates (Age, Country/Region and WT1 mRNA level at Day 1). The model with covariates (WT1 mRNA only) or model without covariates will be also analyzed. In these models, age will be categorized into 3 groups (60 to 64 years, 65 to 70 years, ≥ 71 years), Country/Region into 2 groups (Japan, Republic of Korea+Taiwan), WT1 mRNA into 4 groups (<50, 50-199, 200<= and Unknown).
 - BRESLOW method will be used for ties.
 - Proportionality assumption in Cox proportional hazard model will be assessed using 2 methods:
 - 1) SAS PHREG procedure ASSESS PH option will be used for checking proportional hazard assumption.
 - 2) Look at the log-minus-log survival plots graphically. If the graph results in parallel lines then the proportionality assumption is satisfied.
- HR and its 95% CI at every 3 months interval will be calculated by adding a time varying covariate to Cox Proportional Hazards model as an alternative analysis if the proportionality assumption fails. The model will be as follows:

$$\lambda(t;X) = \lambda_0(t) \exp(\beta_1 \text{trt} * \text{period}_1 + \beta_2 \text{trt} * \text{period}_2 + \dots)$$

where $\lambda_0(t)$ is the baseline hazard function,

trt is the treatment arm(1= OCV-501 and 0= Placebo) and

$$period_1 = \begin{cases} 1 & \text{if } 0 \leq DFS \text{ time} < 3 \text{ Months} \\ 0 & \text{otherwise} \end{cases}$$

$$period_2 = \begin{cases} 1 & \text{if } 3 \leq DFS \text{ time} < 6 \text{ Months} \\ 0 & \text{otherwise} \end{cases}$$

...

So HR (OCV-501 vs. Placebo) for each period will be calculated as follows:

$$\lambda(\text{OCV-501}|\text{period}_k) = \lambda_0(t)\exp(\beta_k)$$

$$\lambda(\text{Placebo}|\text{period}_k) = \lambda_0(t)$$

$$\text{HR}(\text{OCV-501 vs. placebo}|\text{period}_k) = \lambda_0(t)\exp(\beta_k) / \lambda_0(t) = \exp(\beta_k)$$

$$95\% \text{ CI} : [\exp(\beta_k - 1.96 * \sqrt{\text{Var}(\beta_k)}), \exp(\beta_k + 1.96 * \sqrt{\text{Var}(\beta_k)})]$$

- For exploratory purposes, the incidence rate over the entire follow-up period will be calculated using the person-year method by treatment arm as follows.

- 1) Calculate the number of events and person-year at risk by treatment arm.
- 2) Calculate the incidence rates and its corresponding 95% CI by treatment arm. (1 year is calculated as 365.25 days)

$$\text{Rate} = \frac{\text{Number of events}}{\text{Person - year}}$$

95% CI:

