4.11 Subgroup Analysis

1) Definition:

DFS, OS, safety (Summary of TEAE, TEAE by MedDRA SOC and PT) and exploratory parameters will be examined for the following subgroups.

Table 4.11-1 Subgroup	
Factor	Categories
Country/ Region	Japan, Republic of Korea, and Taiwan
Age	60 to 64 years, 65 to 70 years, ≥ 71 years

2) Analysis Set:

FAS for DFS and OS, SS for safety, IRS for Immune response

3) Analysis Method:

For each subgroup, the following statistical analyses will be performed.

DFS/OS: log-rank test, HF test, KM estimates of DFS/OS rate

Safety: Summary of TEAE, Incidences of TEAE by MedDRA SOC and PT

Exploratory parameters: Summary of descriptive statistics

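### DFS and OS are tested separately in six country and age groups, with no estimate of whether the treatment effect differs between the groups

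*Protocol*

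**What the plan says.** Protocol 11.3.7 (Subgroup Analysis) says: "The primary endpoint DFS and secondary endpoint OS will be examined for the following subgroups". The factors are country/region (Japan, Republic of Korea, Taiwan) and age (60 to 64, 65 to 70, 71 and over). Within each level it plans a Kaplan-Meier curve, a hazard ratio with a Wald 95% CI, the 2-year rate and the median.

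SAP 4.11 keeps the same two factors but gives a different list of methods: "DFS/OS: log-rank test, HF test, KM estimates of DFS/OS rate". The subgroup hazard ratio is not in that list, and the change table in SAP 4.13 does not record its removal.

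Protocol 11.3.6 sets the test level: "Two-sided statistical tests will be conducted at the 5% significance level and 95% confidence interval will be provided". SAP 4.2 says that multiplicity is not adjusted. No treatment-by-factor term appears in either document.

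Day 1 WT1 mRNA is not a subgroup factor. It enters the DFS Cox model as a covariate (SAP 4.7.1.1): "treatments effect will be adjusted with covariates (Age, Country/Region and WT1 mRNA level at Day 1". SAP 4.7.2.1 applies the same analysis to OS. SAP 4.7.1.1 codes it in four categories: below 50, 50 to 199, 200 and above, and Unknown. It is a main effect only.

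**The concern.** A subgroup analysis is meant to show whether the treatment effect differs between kinds of patient. Results produced one group at a time do not answer that. Group estimates scatter by chance even when the true effect is the same everywhere. A significant result in one group beside a non-significant one in another is not evidence of a difference. The direct evidence is the ratio of the group hazard ratios with its confidence interval, and the plan does not produce it.

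The SAP list makes this harder for the reader than the protocol list. It offers p-values and survival estimates in each group, without a group hazard ratio to compare. A reader could take a country or age difference from the output when none exists, or dismiss a real one, with nothing in the report to judge it against.

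A smaller, related gap concerns Day 1 WT1 mRNA. The protocol chose consolidated patients because normal "leucocytes will have recovered and there will be fewer leukemia cells in patients who have completed consolidation therapy" (1.2.3). It says of WT1 mRNA that "it is considered to be useful as a monitoring marker of minimal residual disease (MRD" (3.3.3). The marker is already measured and categorised, but a main-effect covariate cannot show whether the treatment effect varies with it. The effect by WT1 level therefore goes unestimated.

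**Working it through.** **Inputs from the documents**
- Placebo 2-year DFS: "the 2-year DFS rate of placebo arm has been estimated to be around 20" per cent (Protocol 11.5). OCV-501 is expected to be 15 to 20 points higher, so 35% to 40%.
- 60 subjects per arm, exponential DFS, two-sided 5% log-rank test, 2-year DFS follow-up (Protocol 11.5, 3.2).
- Enrolment of at most 70 in Japan and about 50 in Korea and Taiwan together (Protocol 11.5).

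**Assumptions**
- Korea and Taiwan split 25/25, with 40/10 as a check.
- Three equal age bands.
- No dropout.

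**1. The plan's own figure**
- Hazard ratio = ln(S1)/ln(0.20). This gives ln(0.35)/ln(0.20) = 0.652 and ln(0.40)/ln(0.20) = 0.569, matching the stated 0.57 to 0.65. These are OCV-501 relative to placebo, although Protocol 11.5 labels them the other way round.
- Events at 2 years = 60 × 0.80 + 60 × (1 − S1) = 87 (S1 = 0.35) and 84 (S1 = 0.40).
- Schoenfeld power is 51.3% and 73.3%. Simulated log-rank power is 51.2% and 73.5%. Both are within 2 points of the stated 53% and 75%.

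**2. Number of subgroup tests in SAP 4.11**
- (3 countries + 3 age bands) × 2 endpoints × 2 tests = 24.

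**3. Group results when the true effect is uniform**

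Simulation of 10,000 trials per setting. A group favours placebo when observed events on OCV-501 exceed expected, which is the same as a Cox hazard ratio above 1.

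| OCV-501 2-year DFS | At least one of 6 groups favours placebo | Some but not all 6 DFS log-rank tests p<0.05 |
|---|---|---|
| 35% | 51% | 66% |
| 40% | 36% | 80% |

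- With no effect (20% in both arms), at least one of the six DFS log-rank tests gives p<0.05 in 27% of trials.
- Repeat runs gave 35% to 37% and 49% to 51% for the first outcome, 65% to 67% and 79% to 82% for the second, and 26% to 28% under no effect. A crude rate ratio in place of the Cox direction gave 35% and 52% to 53%.
- A 40/10 split of Korea and Taiwan gives 55% and 41% for a group favouring placebo, 66% and 82% for mixed significance, and 29% under no effect.
- The largest of the six hazard ratios (crude rate ratios) is at least twice the smallest in about 75% of uniform-effect trials.
- The mixing follows from low power within groups: about 33% to 51% in Japan, 15% to 22% in Korea or Taiwan at 25 each, and 20% to 32% in each age band.

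**4. What an interaction estimate would deliver**
- SE of the log ratio of hazard ratios = √(4/e1 + 4/e2), where e1 and e2 are the events in the two groups.
- Japan against Korea plus Taiwan, with events in proportion 70:50. For 84 events, √(4/49 + 4/35) = 0.443. For 87 events it is 0.435. The 95% CI extends by a factor of exp(1.96 × SE), about 2.3 to 2.4, either side of the estimate.
- Day 1 WT1, with half the events in a low group (assumption) and no effect elsewhere. SE = √(16/84) = 0.436 or √(16/87) = 0.429. Power = Φ(|ln HR|/SE − 1.96), which is about 25% to 26% at HR 0.57 and 17% at HR 0.65. A ratio of about 0.29 to 0.30 is needed for 80% power.
- Simulation with assumed placebo 2-year DFS of 30% in the low half and 10% in the rest, and no effect in the rest:

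| HR in low-WT1 half | Overall log-rank | Log-rank within low half | Interaction |
|---|---|---|---|
| 0.57 | 23% | 38% | 25% |
| 0.65 | 16% | 25% | 18% |
| 0.40 (outside the planned range) | 45% | 71% | 51% |

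Repeat runs put interaction power at 17% to 27% over the planned range.

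**The case against.** The strongest reply is that little rests on these outputs. The protocol synopsis types the trial as exploratory, SAP 4.13 calls the subgroup analyses supplementary, and no decision depends on a subgroup p-value. The protocol list gives hazard ratios with intervals and no subgroup tests, so the mixed-significance figures apply to the SAP list only. All of this stands, and it limits the harm to misreading of the report. It does not supply the missing estimate.

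A second reply is that interaction estimates from 84 to 87 events are too imprecise to help. The imprecision is real. But a wide interval around the ratio tells the reader that the data cannot separate the groups, which a set of separate p-values does not.

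On WT1 the objection is stronger. Day 1 WT1 is not ignored, since the Cox models adjust for it. The rationale for excluding therapy-related disease (Protocol 5.2), "Considering the pharmacological profile of OCV-501 that exerts therapeutic efficiency through boosting immune response", concerns who is enrolled. It does not say that benefit depends on Day 1 WT1 level. The protocol also describes OCV-501 as HLA class II-restricted and collects HLA genotype, so WT1 is one candidate modifier among several. WT1 therefore belongs in the fix as an option only.

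**Conclusion.** The point holds for the subgroup method. Both documents analyse six groups one at a time, neither estimates a difference in effect between groups, and SAP 4.11 lists 24 unadjusted tests without the hazard ratio that Protocol 11.3.7 plans. Under one uniform effect of the planned size, about 35% to 51% of trials would show a group favouring placebo and about 66% to 82% would mix significant and non-significant groups. Under no effect, about 26% to 28% would show at least one DFS p<0.05. These figures rest on the assumed 70/25/25 country split, equal age bands and no dropout. A more uneven Korea/Taiwan split makes a group favouring placebo more likely.

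A reader might go further and infer that an effect confined to patients with low WT1 will be missed because WT1 is left out, or that WT1 is the only effect modifier the mechanism raises. The documents support neither. They do not tie benefit to WT1 level. At HR 0.57 to 0.65 confined to a low-WT1 half, an added interaction test would itself have only about 17% to 27% power, so the main limit is sample size. The higher power at HR 0.40 comes from an effect larger than the plan assumes. What can be said is that the effect by WT1 level goes unestimated.

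**What to change.** Amend SAP 4.11 before unblinding and record the change in the SAP 4.13 table:

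1. For each subgroup factor and for both DFS and OS, fit one Cox model with arm, factor and arm-by-factor interaction.
2. Report each group's hazard ratio with 95% CI, which restores what Protocol 11.3.7 plans. Report the ratio of hazard ratios with 95% CI, and give the interaction p-value as exploratory. State the country coding, since SAP 4.7.1.1 pools Korea and Taiwan while SAP 4.11 keeps them apart.
3. State that differences between groups are judged on the ratio of hazard ratios and not on group-specific p-values.
4. Optionally, add Day 1 WT1 mRNA as a further exploratory factor, using the existing SAP categories or below 50 against 50 and above, with Unknown shown separately.

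The cost is a few lines of SAP text and a handful of outputs from data already collected. SAP 4.13 already records other analyses added to those in the protocol, so the SAP is a sufficient place for this one. The downside is imprecision: the intervals will be wide, and the text should say that the purpose is estimation.
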